2. Examine the preliminary effects of the MOMP intervention on measures of maternal psychobehavioral factors (i.e., depressive symptoms, anxiety, ruminations, PA self-efficacy, attachment) at baseline, midpoint and end of the 12-week intervention, and at 6-weeks postpartum and at 10-20 months postpartum, and on baby♦'s birth weight, compared with archival data from depressed women receiving the UC, to estimate effect sizes to inform future studies.
3. Identify DNA methylation (DNAm) patterns associated with chronic depressive symptoms during pregnancy and investigate whether participation in the MOMP intervention targets these patterns: This aim will be accomplished by evaluating both genome-wide and gene-specific DNAm patterns (e.g., candidate genes putatively related to depression, pregnancy, and mindful interventions: Nr3c1, NGFI-A, FKBP5, BDNF, TrkB, HP1BP3, TTC9B). These patterns will be compared with patterns in recently collected archival data from pregnant women with and without depressive symptoms receiving UC.

3. * Describe the study's background and significance, including citations, or upload a citation list in document upload. Use lay language whenever possible.

Chronic and recurrent depressive symptoms are a significant public health problem.¹ Women with chronic depressive symptoms face significant treatment challenges during pregnancy. Close to 20% of women experience clinically significant depressive symptoms during pregnancy (e.g., feelings of sadness, anhedonia, sleep alterations, and fatigue, among others),² with the majority manifesting a recurrence of symptoms rather than a new onset.³⁻⁵ Although there are numerous pharmacological treatments available for depressive symptoms, data are conflicting with respect to safety of antidepressant medications during pregnancy and there is little research addressing efficacy of non-pharmacological therapies in this population.^{3,6,7} Currently, no therapies are universally effective at decreasing depressive symptoms and uniformly accepted as low obstetrical and fetal risk.^{8,9} Further, many pregnant women are concerned about stigma, side effects, fetal effects, and/or costs of the ♦usual care♦ (UC: antidepressants, psychotherapy) for symptoms and elect to avoid or decrease UC during pregnancy.¹⁰⁻¹⁶ Hence, many women with depressive symptoms remain un- or under-treated.³

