(a) **Depressive symptom severity:** Depressive symptom severity will be evaluated using the Patient Health Questionnaire (PHQ-9), a widely used instrument which has been validated during pregnancy.¹⁶⁹ The PHQ-9 includes self-report items regarding depressive symptoms over the past two weeks. Total scores range from 0-27: 0-4 indicates minimal depression, 5-9 mild depressive symptoms, 10-14 moderate depressive symptoms, 15-19 moderately severe depressive symptoms, and =20 severe depressive symptoms. For analysis purposes, presence of depressive symptoms will be defined as a score =10 on the PHQ9. The PHQ-9 includes a question on suicidal ideation,^{202,203} which will be used for monitoring for adverse events as described in the Protection of Human Subjects section. Because the archival comparison group database includes the Edinburgh Postnatal Depression Scale (EPDS)¹⁸⁰ in the pregnancy and postpartum assessment, we will also administer this survey at the same timepoints. The EPDS is a widely used and validated measure of depressive symptoms, with 10 questions appropriate for the prenatal and postpartum woman; a score =10 (range 0-30) suggests possible depressive symptoms. Guidelines regarding management of participants with depressive symptoms or suicidal thoughts are detailed in the Protection of Human Subjects section but in brief, the researchers will be poised to assess further and make referrals to appropriate community organizations, healthcare providers, or emergency departments in cases of psychological distress (score =20 on PHQ9 and/or suicidal ideation) or physical injury. (b) **Stress:** The Perceived Stress Scale-10 (PSS-10), a widely used, psychometrically sound instrument, will assess the degree to which a participant perceives stress in her life during the past month.¹⁸¹⁻¹⁸⁵ The PSS-10 asks respondents to report about feelings such as unpredictability, uncontrollability, and overloading of stress in their lives; scores range from 0-40; higher scores correspond to a higher perceived stress level.¹⁸⁴ (c) **Anxiety:** Current levels of anxiety (state anxiety) will be evaluated with the State-Trait Anxiety Inventory, Form Y (STA). This study focuses specifically on state anxiety, as this score is sensitive to women's anxiety during pregnancy and is more likely to demonstrate change within an intervention period.^{190,204} This measure yields reliable and valid scores.¹⁸⁷⁻¹⁸⁹ The STA scores range from 20-40, with higher scores representing higher levels of state anxiety. (d) **Rumination:** Rumination, or repetitive self-critical thinking, will be evaluated with the 10-item Ruminative Responses Scale (RRS) which assesses the propensity to ruminate in association with sadness or depression. A psychometrically sound and widely used instrument, the RRS asks respondents to rate how often they experience various aspects of rumination.¹⁹³ The RRS has two factors of brooding (self-critical pondering) and reflecting (emotionally-neutral pondering or brainstorming). (e) **Self-Efficacy for Physical Activity:** The Physical Activity Self-Efficacy Scale (PASES)^{194,195} is an eight question scale which contains items about SM of physical activities and social support regarding PA. This psychometrically sound scale was selected because of its specific focus on SM of PA. Originally designed for adolescents, the wording has been slightly adapted for an adult sample. (f) **Maternal-Fetal/Child Attachment:** The Maternal-Fetal Attachment Scale (MFAS)^{32,198} assesses the extent to which women have an affiliation and interaction with their unborn child (during pregnancy) and their infant (during PP). Maternal depression has a proximal effect on maternal-child attachment,¹⁷ hence it is highly relevant to evaluate attachment in relation to an intervention designed to address depression.

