
Objective Measures: (a) **Epigenetic (DNAm):** Peripheral blood specimens will be collected at baseline (gestation 12-22 weeks) and intervention week 12 (gestation of 24-34 weeks), as summarized in Table 1. The PD and/or RAs will arrange to meet participants to collect the blood and transport samples to the VCU School of Nursing's lab for DNA extraction.

Samples will be shipped to HudsonAlpha for DNA methylation assays. HudsonAlpha will use the following procedures for DNA methylation: genome-wide methylation patterns will be determined using the 450K HumanMethylation Chip (Illumina) according to the vendor's protocol. Briefly, DNA will be extracted from the blood samples using standard techniques (Puregene Isolation Kit; Qiagen). Following bisulfite conversion of the DNA, the methylation patterns of the 485,764 targets (including CpG islands, shores, open sea) interrogated in the 450K array will be determined. To verify the results of the 450K array for targeted regions of interest, single loci methylation-sensitive studies of bisulfite converted DNA will be conducted using standard methods.²⁰⁵ Gene-specific patterns of candidate genes chosen a priori will be closely examined. All samples will be coded prior to deliver to the testing labs. As methylation patterns vary from tissue to tissue, one concern is if the patterns present in white blood cells are reflective of the relevant cumulative epigenetic changes

involved in chronic depressive symptoms. Skepticism regarding the utility of blood for the assessment of conditions having brain/nervous system components has recently been diminished by the observation that comparable DNAm changes induced by environmental/social events occur in multiple tissues.⁷⁵ Based on these findings, Szyf²⁰⁶ noted that the results of recent investigations demonstrate that it is feasible to study behaviorally related DNA methylation signatures in peripheral cells²⁰⁶ (p.334). Given this supporting data, as well as the practical need to collect a minimally invasive specimen for study in this pregnant population, peripheral blood will be used to assess DNAm patterns. (b) Birth weight: At the postpartum visit, mothers will be asked to report the baby²⁰⁶s birth weight.

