Comparison Group Data: Archival data from an existing IRB-approved study (NIMHD2P60MD002256, PI: [name]) includes pregnant women recruited from the VCUHS and area clinics who did not receive the MOMS intervention yet were followed throughout their pregnancies and into the postpartum period, using psychobehavioral, birth weight, and DNAm measures identical to those proposed in this study. The de-identified data will be used to form two age/race-matched comparison groups: (a) positive comparison group (n=40): pregnant women with clinically relevant depressive symptoms receiving the UC; and, (b) negative comparison group (n=40): pregnant women without clinical depressive symptoms. The timelines of these studies align well; as of May 2015, the study has enrolled approximately 135 women (50% AA) with ~15% of the sample endorsing depressive symptoms (unpublished data). Data collection from the total expected sample (n=220) will be completed by early 2017, at which point the proposed study will be ready to derive the comparison groups for analysis. To facilitate longitudinal comparisons across the two studies, the pre-/post-intervention data for the proposed study will correspond to data collected early in the second trimester of pregnancy (approximately 12-22 weeks gestation) and late in second trimester/ early in third trimester of pregnancy (approximately 24-34 weeks gestation) respectively, in the comparison study, represented in Figure 2.

Data Analysis Plan

Aim 1: Evaluate the feasibility and acceptability of the MOMS intervention for chronic depressive symptoms during pregnancy: (a) Data related to recruitment, retention and adherence to the MOMS intervention will be analyzed using descriptive techniques, including percentages and means. The number of participants who complete each time point will be recorded and percentages of the following calculated: persons eligible to participate; persons who signed a consent form; and PA sessions attended, home PA participation, and participant attrition. Reasons for attrition will be described.

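### The archive's own figures give about 33 expected depressed comparators, not 40, and Aim 3's 40 pre/post pairs make no allowance for the attrition that the plan cites

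*Combined protocol and SAP*

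**What the plan says.** The comparison groups are described under Research Description, item 4 (Comparison Group Data) and again under Existing Data/Specimen Details, item 1. Both places define a "positive comparison group (n=40): pregnant women with clinically relevant depressive symptoms receiving the UC" and a negative group of 40, each age/race-matched. On the source, they report that as of May 2015 "the study has enrolled approximately 135 women (50% AA) with ~15% of the sample endorsing depressive symptoms (unpublished data" and that "Data collection from the total expected sample (n=220) will be completed by early 2017".

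The positive group serves two aims. Under Aim 2 the intervention is "compared with archival data from depressed women receiving the UC, to estimate effect sizes to inform future studies". Under Aim 3 the archival 40-versus-40 comparison is step (a), the paired pre/post t-tests in the intervention group (n=40) are step (b), and a three-group comparison (n=120) is step (c).

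On blood sampling, Objective Measures (a) states: "Peripheral blood specimens will be collected at baseline (gestation 12-22 weeks) and intervention week 12". The inclusion criteria recruit 41 women. The sample size justification (Study Population, item 3) gives a target of 40, cites 20-40% attrition from the team's earlier studies in support of the Aim 2 size, and then justifies Aim 3 by a pooled N of 120, with no loss deducted.

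**The concern.** The group size, the archive size and the observed share stand almost side by side, and they do not fit together. Two further conditions come on top. UC receipt can only lower the number available. The background section describes UC as antidepressants or psychotherapy and says that "many women with depressive symptoms remain un- or under-treated", so the reduction could be material. The Aim 3 wording, "archival data from pregnant women with and without depressive symptoms receiving UC", can also be read as routine care, which would remove nobody. The documents give no UC share. Matching cannot add women either.

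The paired n raises a similar question. Forty complete pairs from 41 recruits leaves room for one loss; from the target of 40 it leaves none.

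What is at stake is the precision that a reader expects from the effect-size estimates, which are the stated product of Aim 2, and from the Aim 3 contrasts. The pooled 120 is the size of neither the archival contrast nor the paired contrast.

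**Working it through.** **Inputs.** Share with symptoms about 15%, seen in about 135 women; expected archive total 220; positive group 40 (all from Comparison Group Data). Recruits 41 (inclusion criteria). Target 40 and attrition 20-40% (sample size justification). Paired n 40 (Data Analysis Plan, Aim 3). The plan gives no formula for either 40, so each is checked as a yield.

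**1. Positive comparison group**

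- Expected number: 0.15 × 220 = 33. The stated 40 is not reproduced.
- Share needed: 40/220 = 18.2%.
- Binomial(220, 0.15): central 95% range 23 to 44, which includes 40.

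| True share | P(at least 40 of 220) |
|---|---|
| 12.5% | 0.01 |
| 14% | 0.05 |
| 15% | 0.11 |
| 16% | 0.21 |
| 17.5% | 0.42 |

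The women already enrolled can be taken into account. 0.15 × 135 = 20.25, but the documents give no count, so 20 to 22 cases are tried. The other 85 women must supply the rest. The probability is beta-binomial; each range runs from a Jeffreys to a uniform prior.

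| Cases in first 135 | Needed among next 85 | P(at least 40) |
|---|---|---|
| 20 (14.8%) | 20 (23.5%) | 0.06-0.07 |
| 21 (15.6%) | 19 (22.4%) | 0.12-0.13 |
| 22 (16.3%) | 18 (21.2%) | 0.21-0.22 |

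All of this precedes UC and matching. As an illustration, each 10% of the 33 without UC would remove about 3 more women.

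**2. Complete pre/post pairs**

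A pair needs both blood samples. The plan does not say how much of the 20-40% attrition falls before the week-12 draw, so two cases are shown.

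| Losses before week 12 | From 41 | From 40 |
|---|---|---|
| Half | 41 × 0.9 to 0.8 = 36.9 to 32.8 | 36 to 32 |
| All | 41 × 0.8 to 0.6 = 32.8 to 24.6 | 32 to 24 |

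Attrition of 20-40% of 41 is 8.2 to 16.4 losses. To keep 40 pairs, all but one must come after the draw: 7.2/8.2 = 88% to 15.4/16.4 = 94% of them.

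**3. Effect on precision, in SD units**

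- Between groups, SE = √(1/a + 1/b): 40 vs 40 gives 0.2236; 40 vs 33 gives 0.2352, a ratio of 1.05. The 95% half-width goes from 0.445 to 0.469.
- Paired, half-width = t(0.975, n−1)/√n, in units of the SD of the within-woman differences: 0.320 at 40 pairs; 0.338 to 0.361 at 36 to 32 pairs (6-13% wider); 0.361 to 0.422 at 32 to 24 pairs (13-32% wider).

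**4. Pooled total**

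40 + 33 + 40 = 113 expected, or 41 + 33 + 40 = 114 with all recruits, against 120.

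**The case against.** The strongest objection concerns the 15%. It is interim, rounded and unpublished, with no instrument, cut-off or visit attached. The archive follows women into the postpartum period, so counting symptoms at any visit, or at a lower cut-off, could raise the share above 15%. This stands. A reader might infer that 33 is a ceiling, or that 40 cannot be reached; the documents support neither. The background figure of close to 20% would give 0.20 × 220 = 44, but it describes pregnant women in general and not this archive.

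On the pairs, n=40 can be read as the nominal group size and not as a promise of 40 complete pairs. The attrition range comes from earlier studies and is not tied to the week-12 draw, while follow-up here runs to the postpartum period. This also stands in part. A reader might infer that 25-33 pairs is the expected yield, but that holds only if every loss comes before week 12. What remains is that the paired test uses pairs, that the plan gives no other number for them, and that it makes no deduction for loss. The intent-to-treat retention in the Aim 2 analysis does not supply a missing second blood sample.

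Finally, this is a pilot. Feasibility is the primary aim, power is disclaimed, and every reduced size above exceeds the plan's minimum of 12 observations, which it states for Aim 2. That limits the weight of the point but does not make the stated sizes right.

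**Conclusion.** The concern holds as a minor point. On the plan's own figures, a positive group of 40 is unsupported: the expectation is about 33 before UC and matching, and 40 is unlikely but within the range of chance. This assumes that the 15% carries over to the final 220 and to whatever definition forms the group.

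Forty complete pairs are also improbable unless nearly all losses come after the week-12 draw. The total of 120 inherits the positive-group figure, and it does not justify the archival or the paired contrast.

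The cost in precision is small between groups and moderate for the paired test in the early-loss case. A reader might conclude that the trial cannot meet its main purpose. The documents do not support that: the feasibility and acceptability aim does not depend on any of these numbers.

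**What to change.** 1. In Comparison Group Data, Data Analysis Plan Aim 3, Existing Data/Specimen Details, the sample size justification and the inclusion criteria, replace the positive-group 40 with the actual archive count. Fix the definition before counting. One already exists in Maternal Psychological Measures (a): "For analysis purposes, presence of depressive symptoms will be defined as a score =10 on the PHQ9". Add the visit at which it applies, and keep the UC condition and the matching. Until the count is made, write about 33 expected before UC and matching (range about 23-44), and do not present it as a maximum.
2. Restate the total of 120 in the Aim 3 analysis, Existing Data/Specimen Details and the sample size justification to agree: about 113 expected, or 114 with 41 recruited.
3. In the Aim 3 analysis and the sample size justification, label the intervention 40 as enrolled, state the expected number of complete pre/post pairs after attrition with the assumed timing of losses, and justify Aim 3 by the n of each contrast.

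The cost is wording in five places and one count in an archive that the team can already access through a co-investigator. No participants, samples or design features change; the stated sample sizes become less favourable.

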 Category Continuing 8c Review - Data Analysis	Continuing review of research previously approved by the convened IRB where the remaining research activities are limited to data analysis.
 Category Continuing 9 Review - No Risk	Continuing review of research, not conducted under an investigational new drug application or investigational device exemption where categories 2-8 do not apply but the IRB has determined at a convened meeting that the research involves no greater than minimal risk and no additional risks have been identified.

ID: MS8_HM20006941

View: SF - Research Description

Research Description

1. * Describe the study hypothesis and/or research questions. Use lay language whenever possible.

We will conduct a longitudinal pilot trial of the 12-week "MOMS intervention" (Mindfulness of Movement and Symptoms) in pregnant women with current depressive symptoms (n=41) with the primary aim of determining the feasibility and acceptability of this SM intervention. This interdisciplinary team of nurse scientists, psychologists, a statistical genetics methodologist, and a biostatistician is well positioned to use innovative biobehavioral measures (maternal psychobehavioral measures; genome-wide and gene-specific epigenetic patterns; baby♦'s birth weight) to evaluate the preliminary effects of the MOMP intervention. We will compare these data with recently collected archival comparison group data from an existing study (NIMHD 2P60MD002256; PI: [name]) that has examined the same longitudinal psychobehavioral and epigenetic measures, and baby♦'s birth weight, at the same timepoints in pregnant women with depressive symptoms who are receiving UC (n=40) and women without depressive symptoms (n=40).

2. * Describe the study's specific aims or goals. Use lay language whenever possible.

This pilot study has the following specific aims:

1. Evaluate the feasibility and acceptability of the MOMP intervention for pregnant women with depressive symptoms by: (a) exploring recruitment, retention, adherence, and satisfaction data during the 12-week prenatal intervention and at a 6-week postpartum visit; and (b) evaluating participants♦' experiences after the intervention with a semi-structured interview at the postpartum visit.

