Aim 2: Examine the potential effects of the MOMS intervention on measures of maternal psychological symptoms assessed at multiple time points (Table 1) and on the baby²⁰⁶s birth weight, with the primary variable of interest, depressive symptoms, measured by the PHQ-9. Means, variances and covariances/ correlations along with 95% confidence intervals for each of the three groups (intervention [MOMS], comparison group with depressive symptoms [positive], and comparison group without depressive symptoms [negative]) will be calculated for each of the four study time points (baseline [BL], IW6, IW12, postpartum [PP]). A mixed linear model (MLM) will be fit to the data. The model will include one between-subjects effect (Group: MOMS, positive comparison, negative comparison), one within-subject effect (Time: BL, IW6, IW12, PP), and the interaction between group and time. This model will allow estimation of changes from baseline in levels of psychological symptoms within and between groups at each time point. Possible covariates, such as the initiation of UC (medications, psychotherapy), will be fully explored during analysis. Data from participants who drop out of the intervention will be retained in the analytical portion of the study according to intent-to-treat principles. Correlations will be calculated between baby²⁰⁶s birth weight and group (intervention, positive comparison, negative comparison). Figure 2 summarizes data collection timepoints for the study in relation to the archival comparison group database.

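### Does Aim 2 break down because the text names only the EPDS, not the PHQ-9, as held in the archival comparison data?

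*Combined protocol and SAP*

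**What the plan says.** All places are in the combined protocol and SAP.

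- **Data Analysis Plan, Aim 2** (Research Description, item 4) models MOMS, the positive (depressed) comparison group and the negative (non-depressed) comparison group at baseline, week 6, week 12 and postpartum, with a group-by-time interaction, "with the primary variable of interest, depressive symptoms, measured by the PHQ-9". The aim covers the psychological symptom measures listed in Table 1, and the model is described for psychological symptoms in general.
- **Maternal Psychological Measures, (a)** gives a cut-off: "For analysis purposes, presence of depressive symptoms will be defined as a score =10 on the PHQ9". The printed equals sign is taken as a lost at-least sign, since the inclusion criteria use 10 or more. The same paragraph explains why MOMS women also complete the EPDS: "Because the archival comparison group database includes the Edinburgh Postnatal Depression Scale". It gives 10 as the EPDS score that suggests possible depressive symptoms.
- **Research Description, item 1** describes the archival study as one "that has examined the same longitudinal psychobehavioral and epigenetic measures". **Comparison Group Data** says it was run "using psychobehavioral, birth weight, and DNAm measures identical to those proposed in this study". Existing Data/Specimen Details, item 1, and Study Population, item 4, say nearly the same.
- **Comparison Group Data** says the archival records "will be used to form two age/race-matched comparison groups". The positive group is described as "pregnant women with clinically relevant depressive symptoms receiving the UC". No scale, cut-off or visit is attached to either group.
- **Specific Aim 2** (Research Description, item 2) gives the purpose: MOMS is "compared with archival data from depressed women receiving the UC, to estimate effect sizes to inform future studies".

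**The concern.** A three-group model with the PHQ-9 as its main outcome needs PHQ-9 scores in all three groups. The text names the EPDS as the archive's depression scale and adds it to MOMS for that reason, which invites the inference that the archive has no PHQ-9. The Data Analysis Plan gives the EPDS no named role, rank or fallback status.

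If the PHQ-9 were missing, the main Aim 2 contrast would not exist, and only change within MOMS would be left on that scale. The PHQ-9 cut-off could not be applied to the archive either, so the comparison groups would be formed on a different scale from the one on which MOMS women enter. Regression to the mean could then differ between the two depressed groups and look like an intervention effect, or hide one.

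**Working it through.** **1. The plan's own figures.** Study Population, item 3, gives three groups of 40: 3 × 40 = 120, as stated. With its 20-40% attrition, MOMS completers are 40 × 0.8 = 32 to 40 × 0.6 = 24, both above the minimum of 12 cited there. Nothing in this concern alters those numbers.

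**2. What the model needs.** Group-by-time degrees of freedom = (groups − 1) × (times − 1).
- PHQ-9 in all three groups at four visits: (3 − 1)(4 − 1) = 6.
- PHQ-9 in MOMS only: (1 − 1)(4 − 1) = 0, so no between-group contrast.

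The concern therefore has force only if the PHQ-9 is absent from the archive.

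**3. Is it absent?** The same-measures statements, read literally, include the PHQ-9, and Research Description, item 1, adds that the timepoints match. The sentence on the EPDS says the archive includes that scale. It does not say that it is the only depression scale there. An archive with both scales satisfies every sentence. Table 1 and Figure 2, on which the plan relies for measures and visits, are separate uploads not reproduced in the text. No contradiction can be shown.

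**4. What happens in each case.**
- *PHQ-9 held at matching visits.* The model runs as written and the EPDS is a second depression measure.
- *PHQ-9 not held.* The EPDS is collected in both studies and is a psychological symptom measure, so the same model applies to it. The PHQ-9 gives within-MOMS change.

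Precision in the second case, for a standardised difference at one visit, with half-width t(0.975, n₁ + n₂ − 2) × √(1/n₁ + 1/n₂) and the archival group held at 40 (an assumption):

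| MOMS v positive | Half-width (SD) |
|---|---|
| 40 v 40 | 0.445 |
| 32 v 40 | 0.473 |
| 24 v 40 | 0.516 |

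These widths depend only on the numbers of women. The PHQ-9 would give the same, so they are not a loss from changing scale.

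**5. Forming the archival groups.** The text supplies what is needed: a PHQ-9 cut-off of 10 for analysis, an EPDS cut-off of 10, and an early window of about 12-22 weeks' gestation that Comparison Group Data aligns with the MOMS baseline. Applying the cut-off of whichever scale is held, in that window, is the natural reading.

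**6. Regression to the mean.** Having the PHQ-9 in both studies would not remove this problem. MOMS women qualify at a phone screen whose answers are not kept (Research Description, item 4, Screening; Privacy), and they complete separate baseline questionnaires at Visit 1. Archival women would be selected on their own study score in the baseline window. Suppose, as assumptions, normal scores, selection of the top 15% in both studies (mean 1.554 SD), a screen-to-baseline correlation ρ, the same correlation r of screen and baseline with week 12, and no intervention effect. The archival fall is 1.554(1 − r) and the MOMS fall is 1.554(ρ − r). The difference is 1.554(1 − ρ):
- ρ = 0.95: 1.554 × 0.05 = 0.08 SD
- ρ = 0.85: 1.554 × 0.15 = 0.23 SD
- ρ = 0.75: 1.554 × 0.25 = 0.39 SD

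These are SDs of an unselected population and are not comparable with the half-widths above. The inputs are assumed, so only the direction matters: unequal regression arises even with one shared scale. It comes from comparing a screened cohort with an archive, and naming an outcome scale would not cure it.

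**The case for a change.** The best case for a change is that the check is cheap and the omission is real. The investigator who leads the archival study is a co-investigator here, so its contents could be confirmed in one step. The EPDS was added to link the two studies, yet the analysis section never mentions it. The archival groups lack a stated scale, cut-off and visit even if the PHQ-9 is held, and in a non-randomised comparison a rule chosen after looking at the data is open to doubt.

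Most of these facts stand. The text does not name the PHQ-9 in the archive, the EPDS has no explicit rank, and the grouping rule is not written out. The consequence is smaller than it seems. Which scale can be used is settled by what the archive contains, not by its results: if the PHQ-9 is there it is already named as primary, and if it is not, the EPDS is the scale known to be shared. Some freedom remains in choosing the cut-off and window, but the text already points to one of each. The early-pregnancy selection rule should be reported with the results, as any analyst would do when describing how the archival groups were drawn.

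**Conclusion.** No change to the plan follows. The stated harm, losing the main between-group contrast, depends on the PHQ-9 being absent from the archive. The text does not show that, and its same-measures statements point the other way. If it were absent, no data would be lost: the EPDS is collected in MOMS for comparison with the archive, the Aim 2 model extends to it, and the half-width against usual care is about 0.45-0.52 SD, as for any outcome at those sample sizes.

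What remains is missing detail on scale ranking and group definition, which analysts can fill from material already in the protocol. The study is a pilot whose primary aim is feasibility and acceptability, and the sample size section says it is not powered for effectiveness. Unequal regression to the mean is a genuine limit on interpretation, but it follows from the archival design under either scale. This conclusion assumes that the archive holds the EPDS at visits matching MOMS, as Maternal Psychological Measures indicates, and that the positive group reaches its planned 40.

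### Aim 2 promises a birth-weight effect size against depressed usual-care women, but the planned correlation with a three-level group does not commit to that contrast or an interval for it

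*Combined protocol and SAP*

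**What the plan says.** **The promise.** Specific Aim 2 (Research Description, item 2) covers the effect of the intervention on the psychobehavioral measures and on "birth weight, compared with archival data from depressed women receiving the UC, to estimate effect sizes to inform future studies". That names one comparator, the archival positive comparison group, and one target, an effect size.

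**The analysis.** The Aim 2 paragraph of the Data Analysis Plan contains three elements:

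- Descriptives: "Means, variances and covariances/ correlations along with 95% confidence intervals for each of the three groups", at each of four time points.
- A mixed linear model with group, time and their interaction. Its stated use is: "This model will allow estimation of changes from baseline in levels of psychological symptoms".
- The one sentence that gives a method for birth weight: "Correlations will be calculated between baby"’s "birth weight and group (intervention, positive comparison, negative comparison").

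**The measurement.** Birth weight is obtained once. Under Objective Measures: "At the postpartum visit, mothers will be asked to report the baby"’s birth weight.

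**The groups.** Under Comparison Group Data: "The de-identified data will be used to form two age/race-matched comparison groups", each planned at 40 women. The sample-size justification (Study Population, item 3) gives a target of 40 women in the intervention and past attrition of 20 to 40%. It says that group means and variances will serve to estimate effect sizes, without naming birth weight or a particular contrast.

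**The concern.** The objective is a signed difference between two named groups. The method is a correlation with a nominal variable that has three levels, one of which (women without depressive symptoms) is not in the stated comparison. A correlation of that kind is not defined until someone chooses a coefficient and a coding, and most choices answer a different question.

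Two analysts following the sentence could report a coded r, an eta or a set of pairwise coefficients. Only the last contains the MOMS-versus-positive comparison. The pilot's quantitative purpose is to hand effect sizes to a later trial, and a coded r or an eta over three groups cannot be carried into a two-group design.

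**Working it through.** The plan states no figure for this point, so there is none to reproduce. The check has two parts: which planned analysis could reach the promised contrast, and what the correlation readings estimate.

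**1. Which analysis reaches birth weight**

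- The mixed model is built on change from baseline over four time points. Birth weight has one value and no baseline, so the model does not apply.
- The group-wise 95% intervals are within-group summaries. Even if they cover birth weight at the postpartum visit, they are not an interval for a difference.
- That leaves the correlation sentence.

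**2. One coefficient over three groups, coded 1-2-3 in the listed order**

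Take the within-group SD as 1. The means m are assumptions, since the documents give none. With group shares as weights,

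r = cov(code, m) / [SD(code) × √(1 + var(m))].

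At equal n the codes deviate from their mean by -1, 0 and +1, so cov = (m_neg − m_MOMS)/3. The positive-comparison mean drops out.

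Set m_MOMS = m_neg = 0 and m_pos = −d, so that d is MOMS minus positive. The pairwise point-biserial is d√(pq)/√(1 + d²pq), where p and q are the two group shares. For d = 0.5 and equal groups it is 0.25/√1.0625 = 0.243.

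| MOMS / positive / negative | r over three groups at d = −0.5, 0, +0.5 | Pairwise, MOMS vs positive |
|---|---|---|
| 40 / 40 / 40 | 0, 0, 0 | −0.243, 0, +0.243 |
| 40 / 33 / 40 | 0, 0, 0 | −0.241, 0, +0.241 |
| 24 / 33 / 40 | −0.034, 0, +0.034 | −0.240, 0, +0.240 |

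The 33 is 0.15 × 220, the archival study's share with depressive symptoms applied to its expected size. The 24 is 40 × 0.6, the upper attrition figure applied to MOMS only.

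In row 2 the mean code is (40 + 66 + 120)/113 = 2, so the positive group still carries zero weight. In row 3 the mean code is 210/97 = 2.165. With d = +0.5, cov = (33/97) × (2 − 2.165) × (−0.5) = 0.028, SD(code) = 0.795, √(1 + var(m)) = 1.028, and r = 0.034.

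**3. Other codings, equal n**

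For means 0.3 / 0 / 0.3 (MOMS / positive / negative; d = 0.3), r is 0, +0.12 or −0.12 depending only on how the labels are numbered. For means 0 / 0 / 0.4 (d = 0), r is 0, +0.16 or −0.16.

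**4. Eta, equal n**

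Eta = √[var(m)/(1 + var(m))] needs no coding but has no sign and no direction. A 0.4 SD shift in any one group gives var(m) = 0.16 × 2/9 = 0.0356 and eta = 0.185, whichever group it is. Means 0.3 / 0 / 0.3 give var(m) = 0.02 and eta = 0.140. So eta is larger for 0 / 0 / 0.4, where MOMS minus positive is zero, than for 0.3 / 0 / 0.3, where it is 0.3 SD.

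**5. Precision of the contrast (context only)**

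This follows from sample size, not from the wording. The unadjusted 95% half-width in SD units is t(0.975, n1 + n2 − 2) × √(1/n1 + 1/n2): 0.445 at 40 vs 40, 0.516 at 24 vs 40, 0.469 at 40 vs 33, and 0.538 at 24 vs 33.

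**The case against.** The strongest reply is that the plan says correlations, in the plural. That fits pairwise or indicator-coded coefficients, and one of these would be the MOMS-versus-positive point-biserial. It is signed and converts to a standardised difference given the group sizes. The r = 0 illustration depends on a single coefficient, one coding order and equal MOMS and negative means, none of which the plan states. This stands as a possible reading, but the sentence lists three groups and names no pair.

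Second, the ingredients are promised: group means, variances and intervals in the Aim 2 paragraph, and a link from means and variances to effect sizes in the sample-size justification. The study design text also says birth weight data will be compared with the archival groups. The difference could therefore be worked out by hand. That is true, but none of this text commits to a birth-weight contrast or to an interval for it.

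Third, Existing Data/Specimen Details refers to a section D.8.2 for the full analysis, and no section with that number is in the documents. The contrast may be specified there, so the point is confined to the text available.

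Fourth, this is a feasibility pilot with no claim to power for effectiveness, and the PHQ-9 is the main Aim 2 variable. That limits the weight of the point but does not remove the mismatch between objective and method.

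**Conclusion.** The concern holds on the visible text. Aim 2 names a comparison and an effect size for birth weight. The stated method is ambiguous, and its two single-coefficient readings do not estimate that comparison: a coded r can stay at 0 across a range of −0.5 to +0.5 SD in the contrast, and eta cannot say which group differs. The pairwise reading would serve but is not stated, and no interval for the difference is committed to.

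The size of the problem is modest. Birth weight is an exploratory outcome, no data are lost, and the contrast can be computed from the same dataset. The correlation figures assume a within-group SD of 1 and chosen group means. They show what the coefficients can miss and do not predict the trial's result. This should be corrected, but it does not threaten the study.

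**What to change.** Replace the correlation sentence under Aim 2 with, for example: *Birth weight will be analysed in a linear model with group as a factor, adjusted for the matching factors age and race; the Aim 2 estimate is the MOMS-minus-positive difference in grams and in SD units with a 95% CI, and the contrast with the negative group is secondary.*

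The essential parts are the named contrast and its interval. The adjustment carries the matching factors into the analysis; an unadjusted difference with its interval would also close the gap. If section D.8.2 already specifies the contrast, bring that text into the plan.

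The cost is one sentence and slightly more analysis work, with no new data collection.
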